1.1. Protocol

1.1.1. Title

An Open Label, Single Dose, Bioavailability Study of Topical Transdermal Glucosamine Cream on the Synovial Fluid Tapped from Osteoarthritic Adult, Male and Female Human Subjects already undergoing Arthrocentesis

1.4.3. Role

Independent lab accredited by SAC-Singlas. They will carry out the analysis of glucosamine in the synovial fluid.

2. Background Information

2.1. Investigational product / Test product

2.1.1. Name and description

Topical Glucosamine cream, Lynk Biotechnologies Pte Ltd, TGC® Transdermal Glucosamine Cream Plus Capsaicin containing 10% w/w Glucosamine Sulphate.2 KCl, presented as a finished product.

2.1.2. Manufactured by DynaLynk Pharma Pte Ltd (GMP certified).

2.2. Findings from non-clinical studies and clinical trials that are relevant to the trial.

Osteoarthritis (OA) is the most common form of arthritis which affects 9.6% of men and 18% of women over 60 years old worldwide ^[1,2]. OA is a degenerative disease which causes inflammation of the joints with thinning of the articular cartilage. The cartilage in our joints allows for the smooth movement of joints. When it becomes damaged due to injury, infection or gradual effects of ageing, joints movement is hindered. As a result, the tissues within the joint become irritated causing pain and swelling within the joint ^[1].

Glucosamine is commonly used as a treatment for OA and is commonly available over the counter in local pharmacies without a doctor's prescription ^[1]. OA patients who have failed to respond to analgesics and non-pharmacologic measures and want to try glucosamine may be given glucosamine sulphate 1500 mg once daily as pharmacologic studies suggest that maximal benefit is better achieved at this dose ^[3].

The use of glucosamine for the treatment of Osteoarthritis (OA) has been extensively studied and numerous reports and notable reviews were published in recent years ^[4-6]. Glucosamine is known to have beneficial effects on joint functions by acting as a precursor in the production of glycosaminoglycans, a major component in the cartilage ^[7]. A 3 year randomized placebo controlled double blind study on 202 patients reported a retardation of knee OA ^[8]. A more recent study by Selvan et al. comparing the efficacy of glucosamine with a combination of glucosamine and nonsteroidal anti-inflammatory drugs revealed that both groups have significant improvement in pain, stiffness and physical function ^[9].

While oral dosage of glucosamine has been well established, drug developers are turning to transdermal drug delivery technology, as a way to overcome the negative effects of the passage of the drug through the digestive system ^[7,10]. Transdermal delivery can combine the advantages of IV infusion with the convenience of oral administration.

Traditional studies measured the glucosamine level in blood plasma to predict the efficacy of glucosamine for the treatment of OA. The major shortcoming of this approach is that we have no certainty that the glucosamine is actually delivered to the affected areas that need it. Glucosamine is one of the important basic natural components of cartilage and synovial fluid ^[11]. It is believed that glucosamine may help to stop cartilage breakdown, build cartilage and decrease swelling of the OA joints ^[9].

Unpublished clinical data from Lynk Biotechnologies Pte Ltd studies show that:

- Transdermal Glucosamine Cream (TGC) can deliver glucosamine transdermally in mice. The study demonstrated that the plasma concentration of glucosamine is dose dependent ^[12].
- TGC has shown superiority over the placebo cream, for the treatment of knee osteoarthritis. Significant reduction in pain and increase in mobility was observed after 3 weeks of drug application ^[13].

- TGC can deliver glucosamine transdermally into horses' blood and synovial fluid^[14].

The present study is conducted to assess the bioavailability of glucosamine in the synovial fluid of OA joints, following topical application of a transdermal glucosamine cream.

To our knowledge this is the first study describing the bioavailability of glucosamine in human synovial fluid following the application of a topical cream.

2.3. Summary of the known and potential risks and benefits, if any, to human subjects.

OA patients with swollen knees will normally seek treatment for pain relief by having the synovial fluid extracted (tapped) from the diseased knee by the Clinician. This procedure is independent from the clinical trial. The Clinician will collect as much as synovial fluid as he would have done in a non-clinical trial situation, in order to reduce swelling and relieve the patient from pain. Volume collected will vary depending on the patient's medical condition (typically 5 to 50ml of synovial fluid will be collected).

This trial synchronizes the application of the Test product with the above procedure so that no additional invasive clinical intervention is needed to determine the bioavailability of glucosamine in the synovial fluid.

Therefore the only additional risk brought about by this trial is the risk associated with topical application of the Test product. Based on the history of usage of the Test product over the last 10 years with over 250,000 tubes sold OTC, the only adverse effect reported by the consumers relates to minor rashes over prolonged usage. Less than 10 complaints of this nature have been received over this period.

No health related benefits is being promoted for a single application of the Test product.

2.4. Description of and justification for the route of administration, dosage, dosage regimen, and treatment period(s)

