4.2. Trial design

This is an open label, single dose design to examine the glucosamine content in the synovial fluid after applying the Test product on OA patient's knee.

4.3. Procedure flowchart:

4.4. A description of the measures taken to minimise / avoid bias, including randomisation / blinding:

The analytical results are objective. There is no possibility of subjective bias or placebo effect. Therefore there is no measure necessary and hence no randomization needed.

As for the selection of subjects, there is no need to have measures to minimise bias. There is no bias since we take all patients that come in to the clinic for treatment. Patients are not selected for control or test group, they select themselves by choosing (yes or no) to apply the Test product.

- 4.5. A description of the trial treatment(s) and the dosage and dosage regimen of the investigational product(s). This also includes description of the dosage form, packaging, and labelling of the investigational product(s).

A single dose of 2g of the Test product will be applied topically on the affected knee of the Test Group subjects. The Test product is presented in a white tub, labelled with the product name, Batch Number and Expiry date.

- 4.6. The expected duration of subject participation, and a description of the sequence and duration of all trial periods, including follow-up, if any.

Single session, up to 4 hours, for the cream application and joint's fluid aspiration. The tapping of synovial fluid should be done between 1 and 3 hours following cream application (for the Test group). No follow-up needed.

- 4.7. A description of the "stopping rules" or "discontinuation criteria" for individual subjects, parts of trial and entire trial.

Subjects participation may be terminated if:

- Allergy occurs after cream application and before tapping of synovial fluid
- Non-compliance to any of the exclusion/inclusion criteria

Subjects are free to withdraw at any time, without giving a reason. This will not affect the standard of care they receive.

- 4.8. Accountability procedures for the investigational product(s), including the placebo(s) and comparator(s), if any.

There is no risk of any mix up since there is no comparator or placebo arm in this study.

- 4.9. Maintenance of trial treatment randomisation codes and procedures for breaking codes.

The subjects will be identified via subject ID, a 3 digits number (e.g: 123). Samples will be labelled with the subject ID.

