All serious adverse events (SAEs) that are unexpected and related to the Test product will be reported to HSA. The investigator is responsible for informing HSA no later than 15 calendar days after first knowledge that the case qualifies for expedited reporting. For fatal or life-threatening cases, HSA will be notified as soon as possible but no later than 7 calendar days after first knowledge that a case qualifies, followed by a complete report within 8 additional calendar days.

All reports will be sent to the Clinical Trial Branches (HSA), and other official parties requiring them (e.g: IRB).

The PI will take all appropriate measures to ensure the safety of the patients, including referral to a specialist if indicated.

9. **Statistics**

9.1. A description of the statistical methods to be employed, including timing of any planned interim analysis(es), and the level of significance to be used.

Statistical analysis will be performed using a one-sided Z-test, which will be used to determine if the glucosamine content in synovial fluid obtained from the Test group is significantly higher than the glucosamine content in synovial fluid obtained from the Control group. The statistical evaluation will be determined at $P < 0.01$.

9.2. The number of subjects planned to be enrolled. In multicentre trials, the numbers of enrolled subjects projected for each trial site should be specified. Reason for choice of sample size, including reflections on (or calculations of) the power of the trial and clinical justification.

A total of 240 osteoarthritic adult male and female patients (120 for the Test group, and 120 for the Control group) will be enrolled in this study. It is assumed that under single dose and with this study design the planned number of subjects is sufficient to achieve the objective of the study.

The sample sizes are sufficient to assume normality while generating a meaningful statistical comparison using the Z-test.

This trial relies on the scientific analysis of the synovial fluid collected, from patients. Therefore it eliminates patient's subjectivity and bias. Hence the trial sample size could be correspondingly reduced.

All eligible subjects will be included in the analyses.

9.3. Criteria for the termination of the trial.

Subjects participation may be terminated if:

- Allergy occurs after cream application and before tapping of synovial fluid
- Non-compliance to any of the exclusion/inclusion criteria

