Subjects are free to withdraw at any time, without giving a reason. This will not affect the standard of care they receive.

9.4. Procedure for accounting for missing, unused, and spurious data.

Using glucosamine concentrations ascertained from the standard addition method, the mean absolute deviation method will be used to eliminate outliers. In addition, non-linear results, with $r^2 < 0.95$, will also be discarded. Data from outliers will be excluded from main analysis.

Missing, unused or spurious data: not applicable in this protocol.

9.5. Procedures for reporting any deviation(s) from the original statistical plan (any deviation(s) from the original statistical plan should be described and justified in protocol and/or in the final report, as appropriate).

Any deviation, if any, will be described in the final report.

9.6. The selection of subjects to be included in the analyses (e.g. all randomised subjects, all dosed subjects, all eligible subjects, evaluable subjects).

All subjects that go for treatment and sign consent form will be part of the study. All samples collected will be analysed.

10. Direct Access to Source Data / Documents

For the purpose of ensuring compliance with the Clinical Trial Protocol, Good Clinical Practice and applicable regulatory requirements, the Investigator should permit auditing by or on the behalf of the Sponsor and inspection by applicable regulatory authorities.

The Investigator agrees to allow the auditors/inspectors to have direct access to his/her study records for review, being understood that these personnel are bound by professional secrecy, and as such will not disclose any personal identity or personal medical information.

The Investigator will make every effort to help with the performance of the audits and inspections, giving access to all necessary facilities, data, and documents.

As soon as the Investigator is notified of a future inspection by the authorities, he will inform the Sponsor and authorize the Sponsor to participate in this inspection.

The confidentiality of the data verified and the protection of the patients should be respected during these inspections.

Any result and information arising from the inspections by the regulatory authorities will be immediately communicated by the Investigator to the Sponsor.

The Investigator shall take appropriate measures required by the Sponsor to take corrective actions for all problems found during the audit or inspections.

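### The primary Z-test takes no account of aspirated fluid volume, which spans about tenfold; if concentration falls with volume, this costs power and can bias the comparison in either direction

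*Combined protocol and SAP*

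**What the plan says.** Section 2.3 explains that the clinician aspirates what routine care would call for. It adds: "Volume collected will vary depending on the patient's medical condition", and gives the range as "typically 5 to 50ml of synovial fluid will be collected".

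Section 9.1 states the primary analysis: "Statistical analysis will be performed using a one-sided Z-test". The test is "used to determine if the glucosamine content in synovial fluid obtained from the Test group is significantly higher" than in the Control group, at P < 0.01. No covariate, transformation or volume term is named. The word used there is content, but section 9.4 shows what the laboratory delivers: "Using glucosamine concentrations ascertained from the standard addition method". Concentration is therefore the natural reading of the tested quantity.

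The sample is "120 for the Test group, and 120 for the Control group" (section 9.2), with no effect size, SD or power. Section 4.4 says of the patients that "they select themselves by choosing (yes or no) to apply the Test product" and holds that no measure against bias is needed. Section 4.10 mentions only gender and age, for possible sub-group analysis. It refers to a Data Record Form that is not reproduced, so whether volume is already recorded cannot be seen.

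**The concern.** A concentration is an amount divided by a volume. If glucosamine in the joint behaves even partly like a limited amount spread through the effusion, a knee with 50 ml reads lower than a knee with 5 ml for reasons unrelated to the cream.

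Two separate consequences follow. Spread in volume then adds spread to the endpoint and lowers power, even when the groups are alike. If, in addition, the patients who choose the cream have systematically smaller or larger effusions, the group comparison is shifted. Smaller Test volumes push towards a false increase; larger ones hide a real increase. Volume is tied to the patient's condition and the groups are self-selected, so balance cannot be taken for granted. Nothing in the planned analysis would reveal or correct an imbalance.

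**Working it through.** **The plan's own figure.** The 120 per group cannot be reproduced, because no effect size, SD or power is given. Solved backwards at one-sided 0.01, the detectable difference is (2.326 + 0.842) × √(2/120) = 0.41 SD at 80% power, and (2.326 + 1.282) × √(2/120) = 0.47 SD at 90%.

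**Inputs from the documents.** 120 per group; one-sided 0.01 (z = 2.326); volume 5 to 50 ml, a ratio of 10.

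**Assumptions (not in the documents).**
- Model: log C = constant + δ·group + β·log V + error.
- Slope β = 0 (no relation), -0.5 or -1 (full dilution).
- Error SD 0.5 on the log scale; δ = 0.25 for power and 0 for false positives.
- Volume log-uniform on 5 to 50 ml, so SD of log V = ln(10)/√12 = 0.665. Reading the range as ±2 SD would give 0.576, and as the central 90% would give 0.700.
- For imbalance, Test volumes are divided by 1.2, which is 17% lower (1/1.2 = 0.833); ln(1.2) = 0.182.

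**Log scale, unadjusted (closed form).** SD = √(0.25 + β² × 0.665²); SE = SD × √(2/120); power = Φ(0.25/SE - 2.326); false-positive rate = Φ(|β| × 0.182/SE - 2.326).

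| β | SD | SE | Power | False positives, Test volumes 17% lower |
|---|---|---|---|---|
| 0 | 0.500 | 0.0645 | 94% | 1% |
| -0.5 | 0.600 | 0.0775 | 82% | 12.5% |
| -1 | 0.832 | 0.1074 | 50% | 26% |

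**Log scale, adjusted for log V.** With V measured accurately, the SE returns to about 0.0645 at every slope. Power is about 94% and false positives about 1%.

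**Raw Z-test, the plain reading of section 9.1 (simulated).** Power is about 90%, 74% and 43% at slopes 0, -0.5 and -1. False positives with Test volumes 17% lower are about 1%, 10% and 23%; repeat runs differ by 1 to 2 points. The step from raw to log without adjustment accounts for part of the power gain (43% to 50% at slope -1), and the volume term for the rest (50% to 94%). The outlier rule of section 9.4 is not applied in these runs.

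**Imperfect volume.** Aspirated volume stands in for effusion volume. With reliability 0.7, about 0.3 of the volume bias survives.
- Slope -1: bias 0.3 × 0.182 = 0.055; SD √(0.25 + 0.3 × 0.442) = 0.618; SE 0.0798; false positives Φ(0.69 - 2.326) = 5%.
- Slope -0.5: bias 0.027; SD 0.532; SE 0.0687; false positives Φ(0.40 - 2.326) = 3%.

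**Sensitivity (SD of log V 0.576).** With volume ratios of 1.25 to 1.5, slopes -0.5 to -1 and error SD 0.5 to 0.8, raw Z-test false positives run from about 6% to 89%. At a ratio of 1.5, slope -1 and error SD 0.5, adjustment still leaves 21% at reliability 0.7 and 53% at 0.5. With balanced volumes, or slope 0, the rate stays at about 1%.

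**The case against.** The strongest objection is that no passage says concentration depends on volume. Section 2.2 describes glucosamine as a natural constituent of synovial fluid, and a constituent of the fluid need not be diluted by having more of it. Under the null nothing is delivered, so a false increase needs endogenous glucosamine to fall with volume, volumes to differ between groups, and the difference to run the right way. Larger Test volumes would make the test conservative. This stands: the false-positive figures are conditional, and the imbalance is assumed.

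Second, suppose endogenous concentration is unrelated to volume and the cream adds a fixed amount. Then volume modifies the treatment effect, and one common slope does not describe that. Simulated under this model with balanced volumes, power without and with log volume was 58.5% against 58.9%, 91.2% against 91.7%, and 99.3% against 99.4% for three delivered amounts. With no delivery and the 1.2-fold imbalance, false positives were about 1% either way. So the adjustment gains almost nothing here, but it also loses almost nothing. It does not make the choice of delivery model unnecessary.

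Third, a reader might infer that adjusting for volume removes the noise and the bias. It does not. Residual variance, proxy error and every confounder that acts by another route remain. With a non-volume log shift of 0.2 (about 22%), slope -1, error SD 0.5 and balanced volumes, false positives were 30% for the raw Z-test and 78% after adjustment: the bias stayed while precision improved. That is no reason to keep an imprecise test, but it means that a significant adjusted result does not show the groups were comparable.

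**Conclusion.** The point holds as a conditional weakness of the primary analysis. The documents establish an unadjusted test, a roughly tenfold range of collected volume linked to the patient's condition, and self-selected groups. They do not establish dilution or a volume imbalance. A reader might infer that the planned test has an inflated error rate as it stands; the documents do not support that. Variation in volume alone costs precision and leaves the false-positive rate at 1%.

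The size depends on the unknown slope. At 0 there is no volume problem, and adjustment costs essentially nothing. At -1, under the stated assumptions, power of the raw Z-test is about 43% against about 94% adjusted. A 17% lower Test volume then raises false positives to about 23%, against about 1% adjusted with accurate volume and about 5% at reliability 0.7. This makes volume adjustment a cheap, worthwhile improvement. It is not a repair of the self-selected design.

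**What to change.** Record the aspirated volume in ml for each tapped knee, if the Data Record Form does not already do so, and report its distribution by group. Prespecify as primary a regression of log glucosamine concentration on group and log volume, testing the group coefficient one-sided at 0.01. Keep the unadjusted comparison and the total amount (concentration × volume) as supportive analyses; they help show whether the conclusion depends on how volume is handled.

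The cost is one number per knee, from fluid that is drawn anyway, and one covariate. A volume not written down at the tap cannot be recovered later.

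State three limits in the plan:
- Volume is read after application, so the adjustment assumes the cream does not change it in the 1 to 3 hours before the tap (section 4.6).
- Aspirated volume is an imperfect proxy for effusion volume.
- A common slope does not capture a treatment effect that varies with volume.

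Other bias from self-selection should be described as unresolved.

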2.4.1. Dosage form: topical cream

2.4.2. Dose

Single dose of 2g of the Test Product containing 200mg of Glucosamine Sulphate. 2KCl

2.4.3. Rationale of Dose

2g of Test product contains 200mg of Glucosamine Sulphate.2 KCl which is in the order of magnitude of the usual dosage for oral glucosamine (500mg or 1g). As the knee surface area is limited any dosage of Test product above 2g is not practical for topical application.

2.4.4. Justification for the route of administration

While oral dosage of glucosamine has been well established, drug developers are turning to transdermal drug delivery technology, as a way to overcome the negative effects of the passage of the drug through the digestive system^[7,10]. Transdermal delivery can combine the advantages of IV infusion with the convenience of oral administration.

2.5. A statement that the trial will be conducted in compliance with the protocol, GCP and the applicable regulatory requirement(s).

This Clinical Trial will be conducted in compliance with Singapore guidelines for Good Clinical Practice (GCP) and in compliance with this protocol. The protocol has been reviewed and approved by Temasek Polytechnic Institutional Review Board (IRB).

2.6. Description of the population to be studied.

Osteoarthritic adult male and female patients (21 to 80 years old) fulfilling the inclusion and none of the exclusion criteria (refer to section 5) will be enrolled for this study. **Subjects are recruited from patients who are already seeking arthrocentesis treatment (synovial fluid aspiration) for Osteoarthritis (OA) at the clinic on their own accord.**

Patients diagnosis of Osteoarthritis is based on standard protocol which includes detailed medical history, blood test if necessary, to exclude other causes like RA, gout etc. and confirmed on standing view X Ray findings. Patients will also be graded (stages of OA) based on that X Rays as well. Only those with primary OA will be included. **Diagnosis would be determined during prior appointment(s) with the clinician.**

Evidence of effusion is determined by manual palpation of the knees directly. There is no need to use ultrasound scan to determine the presence of effusion. Basically, if it can be “felt”, it can be tapped.

- Test Group: 120 subjects regardless of gender (Test product topically applied prior to arthrocentesis)
- Control group: 120 subjects regardless of gender (no Test product applied)

